4 STUDY ENDPOINTS

4.1 Primary efficacy endpoint(s)

The TEAR rate during 24-week treatment period is the primary endpoint for this study.

TEAR is defined as either one of the following:

- 1) Subjects who are ADA negative at baseline and become positive at any timepoint post baseline
- 2) Subjects who are ADA positive at baseline and demonstrate 4-fold increase in titer values at any timepoint post baseline visit.

4.2 Secondary efficacy endpoint(s)

The secondary endpoint points are change from baseline to week 24 for the ITT population.

- Change in HbA1c from baseline
- Change in fasting plasma glucose from baseline
- Change in prandial, basal and total daily insulin dose per unit body weight (U/kg) from baseline
- Change in 7-point SMBG profile from baseline

4.3 Safety endpoint(s)

- Incidence of positive antibody response and NAb and change in antibody percentage binding from baseline.
- Impact of ADA on PD parameters, such as FPG, HbA1c, and insulin dose.
- Change in hypoglycemia rate (30 day adjusted) from baseline and incidence of hypoglycemic events.
- Incidence of treatment-emergent adverse events (TEAEs) and serious adverse events (SAEs).
- Incidence of local reactions (includes injection site reaction), systemic reactions.
- Incidence of hypersensitivity and immune mediated adverse events.
- Incidence of device-related safety assessment.

4.4 Exploratory endpoint(s)

Not Applicable.

5 SAMPLE SIZE AND POWER

Approximately 500 subjects with type 1 diabetes will participate in this trial. The sample size estimation is based on primary objective - to demonstrate that immunogenicity as assessed by TEAR rate with MYL-1601D is equivalent to that of NovoLog® during 24-week treatment. The 80% power will be achieved with 250 subjects per treatment arm to demonstrate that 90% confidence interval of treatment difference (MYL-1601D minus NovoLog®) is within prespecified \pm margin (Table 2 of the SAP) (Chow SC et al, 2002; Chow S-C et al 2003). The pre-specified equivalent margin is dependent on the final rate of NovoLog® TEAR rate. No replacement of subject will be performed if subject discontinued prematurely from the study.

Table 2: Margins and 95% CIs with different reference TEAR event rates in 500 subjects

Event Rate for Reference Product	Estimated 95% CI for the Event Rate (n=250)	Margin	Type I error 2 one-sided alpha	Power	Total N
5%	(2%,8%)	5.7%	0.05	80%	500
10%	(6%,14%)	7.9%	0.05	80%	500
15%	(11%,19%)	9.3%	0.05	80%	500
20%	(15%,25%)	10.5%	0.05	80%	500
25%	(20%,30%)	11.3%	0.05	80%	500
30%	(24%,36%)	12.0%	0.05	80%	500
35%	(29%,41%)	12.5%	0.05	80%	500
40%	(34%,46%)	12.8%	0.05	80%	500
45%	(39%,51%)	13.0%	0.05	80%	500
50%	(44%,56%)	13.1%	0.05	80%	500
55%	(49%,61%)	13.0%	0.05	80%	500
60%	(54%,66%)	12.8%	0.05	80%	500

6 ANALYSIS POPULATIONS

6.1 Randomized analysis set

Randomized analysis set include all subjects who are randomized into the study.

6.2 ITT analysis set

The ITT analysis set includes all randomized subjects without being in the site with GCP violation (including subjects who receive incorrect treatment, do not complete the study or do not comply with the protocol or used prohibited medication, randomized but do not take any study drug). The subjects who are in the site with GCP violation will be excluded from ITT analysis set.

6.3 PP analysis set

The PP analysis set includes subjects who complete Week 24, and do not have protocol violations that impact the primary outcome (as detailed in the blind data review (BDR) plan). Subjects who take other fast acting insulin other than assigned study medication such as rescue medication or subject's own insulin will be excluded from PP analysis set. Subjects who are in the site with GCP violation will also be excluded from PP analysis set. The subjects excluded from the PP population will be determined during the blind data review meeting and summarized in the blind data review report.

6.4 Safety analysis set

The safety analysis set includes subjects who take at least one dose of the study medication after randomization and who aren't in the site with GCP violation. For safety analyses, subjects will be categorized according to the treatment that they actually received.

6.5 Run-in analysis set

Run-in analysis set includes all subjects who enrolled into run-in period.

6.6 Protocol deviations/violations and exclusions from analysis sets

All violations and exclusions of subjects from analysis sets will be identified at the Classification Meeting just prior to study unblinding, through clinical review input provided by Sponsor, using the following sources of information:

- Supportive subject listings, provided by the ICON lead statistician ahead of the Classification Meeting, based on data recorded on the electronic case report form (eCRF).
- Protocol Deviation Logs, provided by ICON Medical.

Further, deviations from the protocol will be classified as major or minor.

7 STATISTICAL CONSIDERATIONS AND ANALYSIS

7.1 Derived Variables

The below table provides the list of derived variables for Demographic and baseline characteristics, various duration derivations, drug compliance, baseline derivations and other important derivations applicable for this study.

Table 3.

Variables	Formula
Demographic and Baseline characteristics	
Body mass index (BMI) (kg/m ²)	weight (kg) / [height (m)] ²
Derivation of Duration	
Study day at any visit	Date of interest – date of first dose of study drug. One day is added if this difference is ≥ 0
Extent of Exposure (Days)	Date of last randomized study medication intake – Date of first randomized study medication intake + 1
Extent of Exposure (Weeks)	Extent of exposure (days)/7
Baseline Derivations	
Baseline	Last non-missing value collected prior to the first dose of study medication in treatment period.
Change from baseline	Post baseline value – Baseline
SMBG Derivations	
SMBG excursion	Post-meal blood glucose – Pre-meal blood glucose
Mean SMBG	All BG/7 and average over 3 days
Mean excursion	All excursion values average over 3 days

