7.2 Handling of missing data and outliers

7.2.1 Missing data analysis methods

Missing data will only be imputed in the primary and sensitivity analyses for TEAR rate associated with ADA and other secondary variables that are mentioned in this document. Otherwise, missing data will not be imputed.

Subjects with missing data are either 1) subjects who completely miss post-baseline ADA data or 2) subjects who miss a portion of ADA data and for whom the TEAR positive or negative status cannot be determined. If a subject with partially missing ADA data already

meets the TEAR criteria, the subject is not considered to be a subject with missing data. To minimize any bias due to missing data, multiple imputation will be used to fill in missing values according to either of two TEAR criteria (binary response and continuous titer values) prior to deriving the TEAR and subsequently estimating the treatment difference and 90% confidence interval. Two imputation processes will be used for each of two TEAR criteria among the missing data. For baseline ADA negative subjects, post baseline binary response (positive or negative) will be imputed using logistic regression multiple imputation assuming missing not at random. For baseline positive subjects, missing titer values (continuous values) will be imputed with same treatment group non-missing subjects using pattern mixture model with the complete-case missing values (CCMV) method (Little 1993). In the case where there are sufficient number of retrieved dropouts, that is, if there are 6 retrieved dropout subjects in each treatment group, the missing values in that treatment group will be imputed by modelling the retrieved subgroup data. Retrieved dropout subjects are the subjects who discontinued assigned study treatment but still remain on the study and had their efficacy and safety measurements captured at the planned visits. If less than 6 retrieved dropout subjects in each treatment group, all non-missing subjects within same treatment group will be used to impute missing data by multiple imputation.

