Daily Total insulin: is the sum of all total daily meal time doses and all basal insulin doses over the double-blind treatment period divided by the number of days measured. Similarly to total daily mealtime dose for which less than 3 mealtime doses are recorded, the missing insulin doses will not be considered for the average computation. That is, if either the mealtime doses are recorded less than 3 times or the basal insulin dose is missing for a particular day of collection, total insulin dose will not be computed. The total insulin dose will be computed for the remaining days where basal insulin dose and at least 3 mealtime doses are collected.

All doses will be divided by total body weight (kg) to convert to daily insulin dose (U) per unit body weight (kg). If body weight at that visit is missing, the weight from previous visit will be used.

8.7.3.4 7-Point Self-Monitored Blood Glucose (SMBG) profile

The 7-point SMBG profile recorded via glucometer and transferred by the subject to the diary, measurement will be performed by the subject at home on 3 days (of which 2 days are consecutive) in the week before the visit

The following summaries will be summarized at week 2, 4, 8, 12, 16, 20 and week 24:

Individual 7-Points SMBG:

The over 3-day averages will be performed for the measures taken at:

- Before breakfast
- Two hours after breakfast
- Before lunch
- Two hours after lunch
- Before dinner
- Two hours after dinner
- Just before sleep

Averages will be performed at each visit.

Excursions and averages in SMBG:

The following averages will be computed:

- Morning excursion
- Noon excursion
- Evening excursion
- Overall excursion
- Pre-meal average
- Post-meal average
- (4-point average) pre-meal and bedtime average
- Overall average

The individual excursion values will be obtained by subtracting post-meal values with pre-meal values, it will be applicable for morning excursion, noon excursion and evening excursion on the respective days. For the overall excursion at morning, afternoon and evening, the individual excursion values obtained on each day will be averaged across the three days.

To compute the overall excursion, first the average of the morning, noon and evening excursion within a day will be computed, then the average will be done across the 3 days.

The pre-meal average will be the average of the following timepoints: before breakfast, before lunch, before dinner on each day, then the average will be done over the 3 days.

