The post-meal average will be the average of the following timepoints: two hours after breakfast, two hours after lunch, two hours after dinner on each day, then the average will be done over the 3 days.

The pre-meal and bedtime average will be the average of the following timepoints: before breakfast, before lunch, before dinner, just before sleep, then the average will be done over the 3 days.

The overall average will be the average of all the 7 timepoints during a day. The daily average will not be computed for a day if more than 3 timepoints are missing on a particular day. The overall average will be kept missing if the daily average is missing for all three days. If the average is missing for one or two days, the average of the remaining days will be considered for the computation.

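### SAP Table 3 divides the daily SMBG sum by a fixed 7, although Section 8.7.3.4 computes days with as few as 4 of the 7 readings

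*SAP*

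**What the plan says.** Three parts of the SAP bear on this derivation.

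- **Section 7.1, Table 3 (derived variables).** Mean SMBG is given as "All BG/7 and average over 3 days". The divisor is the number 7, with no condition for missing readings.
- **Section 8.7.3.4 (SMBG profile).** Profiles are taken at home: "measurement will be performed by the subject at home on 3 days (of which 2 days are consecutive) in the week before the visit". The daily quantity is described so: "The overall average will be the average of all the 7 timepoints during a day". A minimum-data rule follows: "The daily average will not be computed for a day if more than 3 timepoints are missing on a particular day". Days with 4, 5 or 6 readings are therefore kept. For missing days the section adds: "If the average is missing for one or two days, the average of the remaining days will be considered for the computation". It gives no matching rule for missing readings within a day.
- **Section 7.2.1 (missing data).** After listing the analyses that use imputation, it says: "Otherwise, missing data will not be imputed". No imputation of SMBG readings is described elsewhere.

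The variable feeds a secondary efficacy endpoint, listed in Section 4.2 as "Change in 7-point SMBG profile from baseline". Under Section 8.7.3 it is analysed with a repeated-measures model that adjusts for baseline and does not impute.

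**The concern.** Table 3 is where a programmer would look for the formula, and its formula is right only for a complete day. On a kept day with fewer than seven readings, a partial sum divided by 7 counts each absent reading as zero glucose. Such code would run without warning. A second programmer working from Section 8.7.3.4 could use the mean of the recorded values and get a different number.

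At stake is the overall SMBG average and its change from baseline. Diary completeness would leak into a glucose measure: a visit with more gaps would show a lower value for reasons unrelated to glycaemic control.

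**Working it through.** The SAP gives no figure to reproduce here, so the check compares the two sections by arithmetic.

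**Inputs.** The divisor is 7 (Table 3). Up to m = 3 readings may be missing on a day that is still computed (Section 8.7.3.4). There are 3 days per visit (Section 8.7.3.4). No SMBG imputation is planned (Section 7.2.1). All glucose levels below are assumed for illustration.

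**One day.** Let S be the sum of the 7 − m recorded readings. The literal Table 3 value is S/7 and the mean of recorded readings is S/(7 − m). Their ratio is (7 − m)/7, so the shortfall is m/7 whatever the glucose level.

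| Missing readings | Ratio | Shortfall | Flat 150 mg/dL (assumed) recorded as |
|---|---|---|---|
| 0 | 7/7 | 0% | 150 |
| 1 | 6/7 | 14.3% | 900/7 = 128.6 |
| 2 | 5/7 | 28.6% | 750/7 = 107.1 |
| 3 | 4/7 | 42.9% | 600/7 = 85.7 |

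With four missing, the day is not computed.

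**Three-day visit mean.** Assume equal levels on all days. If d of the 3 days each lack three readings and the rest are complete, the shortfall is d × (3/7)/3. That is 14.3% for d = 1, 28.6% for d = 2 and 42.9% for d = 3.

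**Change from baseline.** Take a subject whose glucose is truly unchanged at 150 mg/dL.

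- Baseline complete, all three follow-up days lacking three readings: 85.7 − 150 = −64.3 mg/dL, an apparent improvement.
- The reverse: 150 − 85.7 = +64.3 mg/dL, an apparent worsening.
- Both equally incomplete: 85.7 − 85.7 = 0.
- Baseline complete, one of three follow-up days lacking three readings: (85.7 + 150 + 150)/3 − 150 = −21.4 mg/dL.

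These figures show direction and scale for one subject. They are not estimates of a modelled treatment difference.

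**Against the true 7-point mean.** Here it matters which readings are missing. With assumed pre-meal, post-meal and bedtime values of 140, 180 and 160 mg/dL, the true mean is (3×140 + 3×180 + 160)/7 = 160.

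- The three post-meal readings missing: the literal value is 580/7 = 82.9, or 48.2% low. The mean of recorded readings is 580/4 = 145, or 9.4% low.
- The three pre-meal readings missing: the literal value is 700/7 = 100, or 37.5% low. The mean of recorded readings is 700/4 = 175, or 9.4% high.

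So 42.9% is the worst permitted shortfall against a day's own recorded mean, not a bound against the true profile mean. Correcting the divisor removes its own effect but not the effect of which readings were skipped.

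**The case against.** The strongest reply is that Table 3 is shorthand for a complete profile and Section 8.7.3.4 is the operative rule. Allowing days with 4 to 6 readings makes sense only if the average is taken over what was recorded. Dividing a partial sum by 7 amounts to imputing zeros, which goes against Section 7.2.1. It can also be said that a sum of all readings cannot be evaluated when one is absent, so the literal result might be a missing value and not a low one. No SMBG code in the SAP shows a partial sum over 7.

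Much of this stands as evidence of intent. It does not remove the conflict. Section 8.7.3.4 adapts the divisor explicitly for missing days and says nothing about the divisor for missing readings. If incomplete days were set to missing, that would contradict the rule that keeps them.

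A reader might also infer three stronger points, which the documents do not support.

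- **That the average over days has the same fault.** For the overall average, Section 8.7.3.4 already uses the remaining days when one or two are missing. Only Table 3's wording lags behind.
- **That the error would always look like better control, or would favour one arm.** The endpoint is a change from baseline, and incomplete baseline days push it the other way. The open-label design makes unequal diary completion conceivable, but the documents give no completion rates by arm or visit.
- **That the secondary endpoint as a whole could be 43% too low.** That figure is for the worst permitted single day. Section 8.7.3.4 lists seven individual timepoints and eight excursions or averages, and the divisor of 7 touches only the overall average.

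**Conclusion.** The inconsistency is real and small. Followed as written, Table 3 gives a daily value 14.3%, 28.6% or 42.9% below the mean of the recorded readings when 1, 2 or 3 are missing. The shortfall in a visit mean is smaller when other days are complete.

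This rests on two assumptions: that Table 3 is coded as a partial sum over 7, and that its mean SMBG is the same variable as the overall average in Section 8.7.3.4, which appears so but is not stated. It is therefore an unreconciled derivation rule, not proof that the analysis will be biased. How far it would matter depends on how often diary days are incomplete, which the documents do not say. The individual timepoints, the excursions, the other SMBG averages and the primary antibody-response analysis are not affected.

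**What to change.** In Table 3, define mean SMBG as the sum of the day's non-missing readings divided by the number of non-missing readings (at least 4 of 7), then averaged over the available days. Cross-refer to Section 8.7.3.4, and say there that the overall average is this variable. If the derivation has already been programmed, check that the code divides by the count of recorded readings.

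The cost is one line in the SAP and a cross-reference. Data collection, sample size and the primary analysis do not change.

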7.2 Handling of missing data and outliers

7.2.1 Missing data analysis methods

Missing data will only be imputed in the primary and sensitivity analyses for TEAR rate associated with ADA and other secondary variables that are mentioned in this document. Otherwise, missing data will not be imputed.

Subjects with missing data are either 1) subjects who completely miss post-baseline ADA data or 2) subjects who miss a portion of ADA data and for whom the TEAR positive or negative status cannot be determined. If a subject with partially missing ADA data already

meets the TEAR criteria, the subject is not considered to be a subject with missing data. To minimize any bias due to missing data, multiple imputation will be used to fill in missing values according to either of two TEAR criteria (binary response and continuous titer values) prior to deriving the TEAR and subsequently estimating the treatment difference and 90% confidence interval. Two imputation processes will be used for each of two TEAR criteria among the missing data. For baseline ADA negative subjects, post baseline binary response (positive or negative) will be imputed using logistic regression multiple imputation assuming missing not at random. For baseline positive subjects, missing titer values (continuous values) will be imputed with same treatment group non-missing subjects using pattern mixture model with the complete-case missing values (CCMV) method (Little 1993). In the case where there are sufficient number of retrieved dropouts, that is, if there are 6 retrieved dropout subjects in each treatment group, the missing values in that treatment group will be imputed by modelling the retrieved subgroup data. Retrieved dropout subjects are the subjects who discontinued assigned study treatment but still remain on the study and had their efficacy and safety measurements captured at the planned visits. If less than 6 retrieved dropout subjects in each treatment group, all non-missing subjects within same treatment group will be used to impute missing data by multiple imputation.

If baseline value is missing, the missing baseline value will be imputed with multiple imputations (6 imputations) using no missing baseline values from same treatment group. After imputation, the TEAR criteria will then be applied to each imputed dataset to obtain if a subject is TEAR positive or negative, and the treatment difference and 90% confidence interval will be estimated using Wald confidence limit method. The result will be combined over all imputations by SAS PROC MIANALYZE.

Tipping-point analysis will be performed via the method proposed by Liublinska and Rubin (2014). This will include a graphic display to indicate the tipping point analysis for the TEAR status binary outcome. A graphic display (heating map) is used to indicate the tipping point analysis results with missing values as TEAR positive. The treatment differences are presented as values in the heat map. The graph will be displayed to show the sensitivity ranging from missing favour testing treatment to missing favour reference treatment.

For tipping-point analysis, the number of subjects with missing data include 1) subjects who are missing all post-baseline ADA data, 2) subjects with partially missing ADA data whose TEAR status cannot be determined as positive or negative, and 3) subjects who are missing ADA data at baseline. If a subject with partially missing ADA data already meets the TEAR criteria, the subject is not considered as a subject with missing data.

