For continuous-valued ADA titer, missing values prior to the last observed visit will be filled in with MCMC imputation to make the dataset monotone. Missing values after discontinuation will be imputed by regression imputation of the monotone missing dataset. If there are at least 6 retrieved dropouts in each treatment arm, then a pattern mixture model estimated from the retrieved values will be used for regression imputation of missing values. Otherwise, the complete case missing values method will be used. Missing values for the binary response variable will be imputed using a logistic regression multiple imputation model. A monotone missingness pattern will be created by taking a random draw from the binomial distribution with the same probability as the observed responses from the same treatment group at the same visit.

Pattern mixture models will be fit separately for ADA binary response and for ADA titer. Binary response will be imputed using a logistic regression imputation model, while ADA titer will use a continuous-valued regression. Independent variables in the regression will include the values at all prior visits. Each imputation will be repeated 30 times with a seed of 40872021 for ADA binary response and a seed of 41671703 for ADA titer. Code for the multiple imputation analyses is presented in Appendix 10.1.

If baseline value is missing, the missing baseline value will be imputed with six imputations based on binomial distribution using probability of no missing baseline values from same treatment group.

After imputation, the dataset containing the imputed visitwise TEAR positive or negative status binary response and the dataset containing the imputed ADA titer values will be merged by subject, visit, and imputation number. The Week 24 values will then be used to assign the status of TEAR positive or negative, as follows:

If the subject was ADA negative at baseline, then this subject will be considered TEAR positive if any post-baseline observed or imputed value was ADA positive; otherwise, the subject will be considered TEAR negative. The imputed titer values will not be considered in subjects who are ADA negative at baseline.

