                RESP&visit=ranbin(48010557,1,&novrate);
```

```
end;  
run;
```

```
%mend fillin;
```

```
%macro monotone;  
  %do vis=8 %to 13;  
    %fillin(&vis);  
  %end;  
%mend monotone;
```

```
%monotone;
```

STEP 3.

Since SAS will not accept a binary variable as an independent variable in a logistic imputation model, continuous versions of the binary RESP variables. Both the continuous and categorical variables will be used during the regression. In the code below, the logistic regression code is different If there are <6 retrieved dropouts per group versus ≥ 6 .

```
/***/ setup: create numeric versions of binary variables  
***/  
data indata;  
set indata;  
array resps {7} resp0 resp8-resp14;  
array respns {7} respn0 respn8-RESPN14;  
do i=1 to 7;  
  respns{i} = resps{i};  
end;  
run;
```

```
/** step 3: Perform logistic regression imputation */  
  
/** Code to use if >=6 retrieved subjects per arm */  
proc mi data=indata nimpute=30 seed=40872021  
out=outdata;  
class resp8-resp15;  
var resp0n resp8 resp8n resp9 resp9n resp10 resp10n  
resp11  
    resp11n resp12 resp12n resp13 resp13n resp14 resp14n  
resp15;  
monotone logistic (resp8= resp0n) ;  
monotone logistic (resp9= resp0n resp8n) ;  
monotone logistic (resp10= resp0n resp8n resp9n) ;  
monotone logistic (resp11= resp0n resp8n resp9n resp10n)  
;  
monotone logistic (resp12= resp0n resp8n resp9n resp10n  
resp11n) ;  
monotone logistic (resp13=  
    resp0n resp8n resp9n resp10n resp11n resp12n) ;  
monotone logistic (resp14=  
    resp0n resp8n resp9n resp10n resp11n resp12n resp13n)  
;  
monotone logistic (resp15=  
    resp0n resp8n resp9n resp10n resp11n resp12n resp13n  
resp14n) ;  
mnar model (resp8-resp15 / modelobs=(retrieved=1));  
run;
```

```
/** Code to use if <6 retrieved subjects per arm */
proc mi data=indata nimpute=30 seed=40872021
out=outdata;
by trtgroup;
class resp8-resp15;
var resp0n resp8 resp8n resp9 resp9n resp10 resp10n
resp11
    resp11n resp12 resp12n resp13 resp13n resp14 resp14n
resp15;
monotone logistic (resp8= resp0n) ;
monotone logistic (resp9= resp0n resp8n) ;
monotone logistic (resp10= resp0n resp8n resp9n) ;
monotone logistic (resp11= resp0n resp8n resp9n resp10n)
;
monotone logistic (resp12= resp0n resp8n resp9n resp10n
resp11n) ;
monotone logistic (resp13=
    resp0n resp8n resp9n resp10n resp11n resp12n) ;
monotone logistic (resp14=
    resp0n resp8n resp9n resp10n resp11n resp12n resp13n)
;
monotone logistic (resp15=

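### The retrieved-dropout imputation is not limited to values missing after treatment was stopped, so end-of-follow-up gaps in on-treatment subjects are filled from subjects who stopped the drug

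*SAP*

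**What the plan says.** The donors are defined in SAP 7.2.1: "Retrieved dropout subjects are the subjects who discontinued assigned study treatment but still remain on the study". The branch opens "if there are 6 retrieved dropout subjects in each treatment group", and then "the missing values in that treatment group will be imputed by modelling the retrieved subgroup data". Protocol 7.2.2 carries the same rule. Neither place limits it by the reason for a missing value or by whether the subject was still taking the assigned insulin.

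SAP 8.7.2.1 is narrower. For titers, "missing values prior to the last observed visit will be filled in with MCMC imputation to make the dataset monotone". The next step reads "Missing values after discontinuation will be imputed by regression imputation of the monotone missing dataset", and with at least 6 retrieved dropouts per arm "a pattern mixture model estimated from the retrieved values will be used for regression imputation of missing values". For binary ADA, "A monotone missingness pattern will be created by taking a random draw from the binomial distribution with the same probability as the observed responses" in the same arm at the same visit.

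In the branch with at least 6 retrieved dropouts, the binary code in SAP 10.1.1 step 3 uses "mnar model (resp8-resp15 / modelobs=(retrieved=1", and the titer code in 10.1.2 step 3 has the same option. `RETRIEVED` is a subject-level flag, set only for subjects who discontinued treatment.

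**The concern.** Retrieved dropouts are sensible donors for values missing after treatment was stopped. They are poor donors for someone still taking the assigned insulin. Under protocol 4.2.3 they have moved to marketed insulin, and protocol 5.7 lists, for MYL-1601D subjects who meet the rescue criterion, a switch to study NovoLog as one option. The code never uses on-treatment subjects as donors in this branch, but nothing stops them from being recipients.

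What is at stake is the primary equivalence analysis. SAP 8.7.2.1 names Visit 15 as its basis, and Visit 15 is where an unfilled on-treatment gap reaches the retrieved-dropout model by both the binary and the titer route. The general rule, the detailed rule and the code also differ, so two programmers could obtain different primary results from the same data.

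**Working it through.** **Routing.** ADA samples after baseline are due at Visits 8 to 13 and 15; Visit 14 is a telephone contact. Each pattern below was followed through SAP 8.7.2.1 and the code for the branch with at least 6 retrieved dropouts per arm. The routing was read from text and code; PROC MI was not run.

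| Subject and gap | Text of 8.7.2.1 | Titer code (10.1.2) | Binary code (10.1.1) |
|---|---|---|---|
| On treatment, misses V10 only | MCMC (titer) or arm-and-visit binomial draw (binary) | MCMC | Not pre-filled; left to the retrieved-dropout model |
| On treatment, misses V15 only | No rule: not an earlier gap and not after discontinuation | Retrieved-dropout model | Retrieved-dropout model (the pre-fill loop ends at V13) |
| On treatment, misses V13 and V15 | No rule | Retrieved-dropout model for both | V13 binomial draw; V15 retrieved-dropout model |
| Stopped after V11, no later samples | Regression step, retrieved-dropout model | Retrieved-dropout model | V12 and V13 binomial draw; V15 retrieved-dropout model |

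Row 2 is the clearest case. A baseline-negative subject who is negative through V13 has undetermined TEAR status, so SAP 7.2.1 counts the subject as missing. No pre-fill applies, and V15 is imputed from subjects who stopped.

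The binary column shows a related error. `EMPTY` is 0 when a later value exists and 1 when none does, and the code fills the 1s. It therefore pre-fills trailing gaps and leaves intermittent ones, the reverse of the text. Also, the two PROC MI calls for this branch have no BY treatment statement, unlike those for fewer than 6, so donors are pooled over arms although the text speaks of one treatment group.

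**The plan's own figures, for scale.** The margin is (z0.95 + z0.90) × √(2p(1−p)/250), with the quantiles used in the SAP 10.2 code.
- p = 5%: 2.926 × √(2 × 0.05 × 0.95/250) = 5.70 points.
- p = 20%: 2.926 × √(2 × 0.20 × 0.80/250) = 10.47 points.
- p = 50%: 2.926 × √(2 × 0.50 × 0.50/250) = 13.09 points.

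All 12 rows of SAP Table 2 agree within 0.05 points, and 2Φ(margin/SE − z0.95) − 1 gives power of 79.5% to 80.6%, as stated. The finding does not change these figures.

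At a 20% NovoLog rate (50/250) with complete data, an observed excess of 10/250 gives an upper 90% limit of 10.09 points and passes. An excess of 11/250 gives 10.51 and fails. Equivalence is therefore lost at an observed difference of 4.4 points.

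**Possible size.** The documents give neither the share of an arm with an undetermined TEAR status through a trailing on-treatment gap, nor the difference in imputed TEAR probability between the two donor groups. Both are assumed. Shift in the arm's TEAR rate = share × difference:

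| Share of arm | 10 points | 20 points | 30 points |
|---|---|---|---|
| 1% | 0.1 | 0.2 | 0.3 |
| 2% | 0.2 | 0.4 | 0.6 |
| 5% | 0.5 | 1.0 | 1.5 |

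The largest cell is about a third of the 4.4 points of room (1.5/4.4 = 0.34).

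**The case against.** The strongest reply is that SAP 8.7.2.1 already shows the intent, since it speaks of values after discontinuation, and that the appendix holds example code. This stands as evidence of intent. It does not settle the matter, because 7.2.1 and protocol 7.2.2 say something broader, the code follows the broader rule, and no section says how to fill an on-treatment gap at the end of follow-up.

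The case is also narrow. It needs 6 retrieved dropouts in each arm and an on-treatment subject not yet TEAR-positive. SAP 8.1 lets an unscheduled or end-of-treatment value stand in for a missing scheduled one, and the Visit 15 window runs from day 162 to day 182. This stands and limits the size.

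The sensitivity analyses (no imputation, missing MYL-1601D subjects set to TEAR-positive, and the tipping-point grid) help to bound the effect. They do not correct the primary estimate.

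Three stronger readings are tempting but not supported:
- *That every missing ADA value in the arm comes from retrieved dropouts.* Earlier titer gaps go to MCMC, missing baselines are imputed from observed same-arm baselines, and subjects already meeting TEAR are not treated as missing. The text also exempts intermittent binary gaps; only the reversed flag sends them to the retrieved-dropout model.
- *That this draws the arms together and favors equivalence.* Donors who switched insulin, and donors pooled over arms, make that conceivable. But donors were exposed to their assigned product before stopping, a handful of donors can move a rate either way, and no figure in the documents fixes the direction.
- *That with 6 donors, one or two positives mean an imputed probability of one sixth or one third.* The model conditions on all earlier visits, so what counts is new conversion at the missing visit given a negative history. As coded, at least 12 donors are pooled.

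**Conclusion.** The point holds in a limited form. In the branch with at least 6 retrieved dropouts per arm, SAP 7.2.1, protocol 7.2.2 and the step 3 code do not confine the retrieved-dropout model to values missing after discontinuation, while SAP 8.7.2.1 appears to. On-treatment subjects with trailing gaps, above all at Visit 15, are then imputed as though they had stopped treatment.

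The effect is probably modest and its sign is unknown. The 0.1 to 1.5 points on one arm's TEAR rate is a range over assumed inputs, not an estimate. It would be unlikely to decide the trial unless the result lay near the margin. It does affect the primary analysis and can be avoided, so it should be corrected before that analysis is run.

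**What to change.** In SAP 7.2.1 and 8.7.2.1, in protocol 7.2.2 and in the code of SAP 10.1.1 and 10.1.2:

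- Define treatment status by visit. The subject-level `RETRIEVED` flag cannot make this distinction.
- Apply the retrieved-dropout model only to visits after discontinuation of assigned treatment, with donors from the same arm. Add the missing BY treatment statement to both PROC MI calls for this branch.
- Impute values missing while on assigned treatment, including gaps at the end of follow-up, from same-arm on-treatment subjects.
- Correct the `EMPTY` flag so that the binary pre-fill acts on intermittent gaps, as the text says.

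No new data are needed: SAP 7.1 already uses the date of last randomized study medication intake. The cost is a small amount of extra programming and a text change, and the protocol sentence can be aligned in the same update.
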